Blood samples will be obtained serially in order to determine the immune response against the gp100(g209-2M) and MAGE-3 vaccines (weeks 0, 2, 4, 8, 12, 16, 20, and 24: weeks 8 and 16 will not be collected when leukapheresis is performed; blood samples will be collected by leukapheresis at weeks 0 and 8 (+/- 1 week), and 16 when feasible). To evaluate the inflammatory infiltrate at the site of immunization, biopsies will be obtained of vaccination sites as outlined in section 7.3

Subjects in the adjuvant cohort.

Vaccination will continue for the designated 8 weeks. Blood draw and pheresis times will be the same as subjects in the metastatic disease cohorts. Subjects will be monitored for disease recurrence, but if recurrence occurs prior to the completion of blood draws or pheresis these tests can still be obtained if deemed valid by the PI.

Subjects in the metastatic disease cohort:

At the end of 8 weeks, we will allow tumor progression since patients will have only received vaccine at this point. We estimate that of a total of approximately 24 patients in this cohort, 17% will drop off at this point, leaving a total of 20 patients to be treated in Part 2. To have enough patients to evaluate the secondary endpoints, 20 additional patients may be enrolled in the metastatic disease cohort so that at least 30 patients (10/arm) with gel and 10 are available for Part 2.

At the end of 8 weeks of vaccine, cutaneous lesions (at least 2 and up to 10 lesions) will be assigned by the physician according to region to receive or not to receive 0.2% R848 gel. The CORe randomization system will not be used in Part 2. The physician will designate the regions and which tumors will be treated. The area of cutaneous lesions will be divided into two regions, Region A and Region B, striving to equalize tumor burden in each designated region as best as possible. When feasible, Region A will be a proximal group of lesions, and B distal. When this proximal – distal differentiation is not feasible because of the characteristics of the metastatic pattern, then A and B will be assigned to regions in no particular order. If the two regions coalesce during the vaccination phase, the coalesced tumor may be divided into two regions. Each target tumor whether it is treated or untreated will be marked, measured and photographed for the medical record. Because this dose provides the highest level of immune cell

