**Vaccine biopsies:** Vaccine sites will be biopsied from all patients in the study when feasible. The vaccine site biopsied will be a GP100 vaccine site. The vaccine site will be identified and a punch biopsy taken of full thickness skin with standard sterile technique and closure. Vaccine sites will be biopsied at 24 hrs (+/- 6 hours) after the first gp100(g209-2M) vaccine and at week two of vaccination. These biopsies will occur the day following the vaccination for that week. Failure to obtain vaccine biopsies due to refusal, discretion of the investigators or infeasibility will not constitute a violation of the trial.

**Tumor biopsies** will be taken from patients in the cohort with metastatic disease. There will be no tumor biopsies in patients enrolled in the adjuvant cohort. The first

biopsy will be taken as a base line at any time after enrollment onto the trial, but prior to the first vaccination. A second tumor biopsy will be taken at week 8 prior to the first dose of R848 on the tumors, and at week 12 (4 weeks after initiating R848 therapy on the tumors, but at any time during that week) Tumors will be randomly selected when biopsied, but when feasible, a biopsy will be taken of both a treated lesion and untreated lesion at week 12. Tumor biopsies may be taken using any biopsy method to optimize tumor yield using standard sterile techniques. Tumor volume may not allow for all biopsies to be obtained in all individuals, in this case pre-vaccine biopsies and week 12 will take precedence. Tumor biopsies are at the option of the enrolled subject and the investigators, and failure to obtain tumor biopsies due to refusal, inadequate remaining tumor volume, discretion of the investigators or infeasibility will not constitute a violation of the trial.

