### **Overview of Analysis of Secondary Endpoints**

In addition to the Part 1 and Part 2 primary endpoints described above, several additional secondary endpoints will be investigated. Blood will be drawn at baseline, 2, 4, 8, 12, 16, 20, and 24 weeks, and every 4 weeks after the 24-week draw. A secondary analysis for data generated from Part 1 will measure *ex vivo* IFN- $\alpha$  via ELISPOT assay. This outcome is measured as a continuous variable. Our first step will be to plot each laboratory parameter over the 24 weeks of follow-up to visually inspect the data for any interesting trends between the two clinical trial arms. Separate graphical displays will be created for each treatment arm (gp100(g209-2M)/MAGE vaccine+R848 and gp100(g209-2M)/MAGE vaccine alone). Subsequent to the initial exploratory data analysis discussed above, a repeated measures model will be fit for each measured parameter in the blood to the data using Proc Mixed in SAS to model the repeated laboratory measurements over the 24 weeks of follow-up. Tumor biopsies will be taken as outlined in section 7.3. In addition, a punch biopsy will be taken at the vaccine site for all patients as outlined in section 7.3. To evaluate the ability of **locally administered** TLR agonist (R848 gel) to activate innate immune cells at the **vaccine site** we will evaluate the inflammatory microenvironment at the site of the immunization. Immune cell infiltration for pDCs, mDCs, NK cells, and T-cells will be measured along with immune cell function using IHC and quantitative RT-PCR (qRT-PCR) by Core B. For each patient, changes from baseline will be calculated for both the lesions treated with R848 and for the non-treated lesions. The 4 immune cell infiltration measures and qRT-PCR relative expression measures are all continuous variables. We will use Wilcoxon signed rank test to compare the measures between the lesions within patient. Significance will be assessed at the 5% level.

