To evaluate the ability of R848 gel, administered at the tumor site to induce inflammation and up-regulation of adhesion molecules on tumor vasculature we will focus on the tumor biopsies taken in R848 treated and untreated tumors at pre and post-treatment timepoints outlined in section 7.3. These biopsies will be used to investigate the effect of R848 treatment on tumors compared to untreated tumors. We will measure inflammation and activation of tumor vasculature using Immuno-histochemistry (IHC) and flow cytometry (FACS). We will use mixed models to assess differences between treatment groups. Our mixed model will include fixed effects for treatments, and random effects for

time, treatment-by-time interaction and an additional random effect to model the within patient variability. Significance will be assessed at the 5% level.

To evaluate the ability of R848 gel, administered at the tumor site to enhance immune-cell infiltration into tumor we will utilize antibodies to PDC, mDC, NK, and T cells. Since these are continuous measures (assessed at baseline, 2, 4, 8, 12, 16, 20, and 24 weeks, and every 4 weeks after the 24-week draw) we will use mixed models to assess differences between treatment groups. Our mixed model will include fixed effects for treatments, and random effects for time, treatment-by-time interaction and an additional random effect to model the within patient variability. Significance will be assessed at the 5% level.

To evaluate the ability of R848 gel, administered at the tumor site to generate T-cells against additional tumor antigens, not present in the vaccine (i.e., antigen spreading) we will assess cytokine production against de novo antigens. Since these are continuous measures (assessed at baseline, 2, 4, 8, 12, 16, 20, and 24 weeks, and every 4 weeks after the 24-week draw) we will use mixed models to assess differences between treatment groups. Our mixed model will include fixed effects for treatments, and random effects for time, treatment-by-time interaction and an additional random effect to model the within patient variability. Significance will be assessed at the 5% level.

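### The secondary tumour-biopsy model makes treatment-by-time random and leaves treatment coding unstated, so the R848 effect on lesions may be diluted; the visits, comparator and timing around it also need correcting

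*Combined protocol and SAP*

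**What the plan says.** Section 11.0, Overview of Analysis of Secondary Endpoints, uses one model sentence for three objectives: tumour inflammation and vascular adhesion molecules (B.i), infiltration (B.ii) and antigen spreading (B.iii). It reads "Our mixed model will include fixed effects for treatments, and random effects for time, treatment-by-time interaction", plus a further random effect for within-patient variability.

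- **B.i data:** biopsies from "R848 treated and untreated tumors at pre and post-treatment timepoints outlined in section 7.3". The markers are described as "We will measure inflammation and activation of tumor vasculature using Immuno-histochemistry (IHC) and flow cytometry (FACS)".
- **B.ii and B.iii visits:** "assessed at baseline, 2, 4, 8, 12, 16, 20, and 24 weeks, and every 4 weeks after the 24-week draw".
- **Biopsy schedule (section 7.3):** one biopsy before the first vaccination, then "A second tumor biopsy will be taken at week 8 prior to the first dose of R848 on the tumors, and at week 12". On lesion choice: "Tumors will be randomly selected when biopsied, but when feasible, a biopsy will be taken of both a treated lesion and untreated lesion", the last part referring to week 12.
- **Lesion allocation:** section 6.0 has the physician designate the regions and states "The CORe randomization system will not be used in Part 2". The section 11.0 Overview says that at least one lesion is assigned to R848 at random.
- **Part 2 analysis (section 11.0):** a paired t-test on change from baseline for infiltration and cytokine expression, used if there is no evidence of a Part 1 arm effect. The sample-size argument is a two-sample t-test with 10 per arm and 1.2 SD, at 8 weeks.

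**The concern.** Two of the three scheduled tumour biopsies precede any gel on the tumours. If treatment labels a lesion at all its visits, a treated and an untreated lesion should differ only at week 12, and that difference is a treatment-by-time contrast. A mean-zero random interaction yields a variance. It neither estimates nor tests the R848 effect. The fixed treatment term that remains is an average over visits, most of them before gel.

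The stake is greatest for B.i. The vasculature markers have no other stated analysis, so a real effect could be missed. Infiltration and cytokine expression also have the Part 2 paired t-test, although that is conditional. A signed-rank sentence, "We will use Wilcoxon signed rank test to compare the measures between the lesions within patient", stands in the vaccine-site paragraph, and its scope is unclear.

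Four neighbouring statements do not fit the design either: the visits for B.ii, the comparator for B.iii, the Part 2 time point, and how lesions are allocated to gel.

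**Working it through.** **1. The plan's own figure.** Section 11.0, Part 2: one-sided 5% two-sample t-test, 10 per arm, 1.2 SD. The noncentrality is 1.2 × √(10/2) = 2.68 on 18 df, which gives 82.5% power. The stated 80% is sound. The time point is not: study week 8 precedes tumour gel, and eight weeks of gel (week 16) has no tumour biopsy. At best the sentence describes the Part 1 arms at the week-8 biopsy.

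**2. What the treatment term estimates.** Let the effect be 1 at week 12 and 0 before.
- Label coding, both lesions at weeks 0, 8 and 12: (0 + 0 + 1)/3 = 1/3.
- Label coding, both lesions at one pre-gel visit and week 12: (0 + 1)/2 = 1/2.
- Label coding, one random lesion per pre-gel visit, both at week 12: ignoring within-patient correlation, 20 patients give 20 treated-label samples at week 12 and an expected 10 at each pre-gel visit. That is 20/30 = 0.67 with one pre-gel visit and 20/40 = 0.50 with two. Generalised least squares with assumed variance shares and random terms nested in patient gives about 0.67 to 0.80 and 0.50 to 0.66. More patient-by-visit variance would retain more. Random terms shared across patients would retain less (about 0.34 to 0.75).
- On/off coding: 1. Gel is then present at only one biopsy time, so a treatment-by-time term cannot be separated from treatment.
- One pre-gel-to-week-12 change per lesion: 1.

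**3. Power.** Assumptions: 20 pairs, week-12 effect 1.0 lesion SD, one-sided 5%, no persistent lesion difference, random terms nested in patient. The documents give no lesion correlation ρ, so 0 and 0.5 are shown. Noncentral t on 19 df:

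| Contrast | Effect ÷ SD of contrast | Power, ρ = 0 / 0.5 |
|---|---|---|
| Paired, week 12 only | 1/√(2(1−ρ)) | 92% / 99.6% |
| Label term, three visits | (1/3)/√(2(1−ρ)/3) | 55% / 80% |
| Label term, one pre and one post | (1/2)/√(1−ρ) | 70% / 92% |
| Change from mean of two own pre-gel samples | 1/√(3(1−ρ)) | 80% / 97% |
| Change from one own pre-gel sample | 1/√(4(1−ρ)) | 70% / 92% |

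With one pre-gel and one week-12 sample, the label term and the change score have equal power.

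**4. Pre-existing lesion difference, no R848 effect.** If treated lesions differ by 0.25 SD in the same direction on average, the week-12-only test rejects in 19% / 29% and the three-visit label term in 37% / 59%. If the direction is random across patients, both stay near 5%. Change from the lesion's own sample stays at 5% either way.

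**5. Paired restatement of Part 2.** At 80% power and one-sided 5%, the detectable effect is 0.85, 0.58 and 0.46 SD of the difference for 10, 20 and 30 complete pairs. At 20 pairs, 0.577 × √(2(1−ρ)) is 0.82 lesion SD at ρ = 0 and 0.58 at ρ = 0.5. The plan's 1.2 SD is therefore conservative.

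**6. Passages side by side.**
- *B.ii:* the listed visits are the blood draws. Section 7.3 biopsies tumours only at baseline, week 8 and week 12.
- *B.iii:* the outcome is per patient, and every Part 2 patient has a gel-treated lesion. No randomised group lacks tumour gel, and Arm A versus Arm B would test gel at the vaccine site. The adjuvant cohort has the same draws and no tumour gel, but is not a randomised comparator.
- *Allocation:* physician designation (section 6.0) and random assignment (section 11.0 Overview) cannot both hold as written.

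**The case against.** The strongest reply is that the plan may never have meant a lesion label. On/off coding, or changes as in Part 2, would carry no dilution. This stands, and the concern is conditional on it. The B.i wording about treated and untreated tumours at pre-treatment times nevertheless fits a label, and no coding is written down.

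Second, the one-third figure needs both lesions sampled at all three times. Section 7.3 asks for both lesion types only at week 12 when feasible, gives the pre-vaccine and week-12 biopsies precedence, and selects tumours at random. Regions are designated only at the end of week 8. This also stands: one third is the worst sampling pattern, and with one pre-gel and one week-12 sample there is no power loss against the change score.

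Third, a reader might infer that physician designation inflates false positives. The documents do not support this. Either region may receive gel, section 6.0 strives to equalise tumour burden, and section 11.0 stratifies by lesion size. Bias needs a difference in a consistent direction.

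Fourth, change from the lesion's own sample may often be unavailable, and it is weaker than the week-12 test when lesions are comparable. Both points are true, so the remedy uses it only where such a sample exists.

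**Conclusion.** The concern holds in conditional form and should be fixed. Under label coding, the stated model has no fixed term for the R848 effect on lesions. Its treatment term keeps between 1/3 and about 0.8 of the week-12 effect, depending on which lesions are biopsied before gel. The model problem applies to B.i and B.ii alike. B.i's vasculature markers are the most exposed, having no other stated analysis.

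The B.ii visits, the B.iii comparator, the 8-week time point and the allocation conflict need correction whatever the coding.

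A reader might also infer that Part 2 is underpowered or that the primary comparison is affected. Neither follows: the 1.2 SD figure is arithmetically right, and the Part 1 primary test does not use this model. Lesion correlation, variance shares and the 1.0 SD effect are assumptions, because the documents give none of them.

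**What to change.** - **B.i and B.ii model:** make lesion label, time and treatment-by-time fixed. Use a random patient intercept, and a lesion intercept where the same lesion is re-biopsied.
- **Test:** the within-patient treated-minus-untreated contrast at week 12, using change from the lesion's own pre-gel sample where one exists. Otherwise report the week-12 difference separately, labelled as assuming comparable lesions.
- **B.ii visits:** use the section 7.3 biopsy times.
- **B.iii:** analyse within-patient change from week 8 to later draws, labelled uncontrolled. The adjuvant cohort can be shown beside it as a non-randomised reference.
- **Part 2 sample size:** restate as a paired week-12 comparison for 10, 20 and 30 complete pairs, with lesion correlation stated as an assumption. Reconcile the expected pair count with section 6.0.
- **Allocation and biopsies:** reconcile section 6.0 with the section 11.0 Overview, and state in section 7.3 whether the same lesion is re-biopsied.

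The cost is wording and model code, with no new biopsies or visits. Change scores are available only where the same lesion was sampled before gel. If lesions have no persistent difference, they also cost some power: with two own pre-gel samples and 20 pairs, 80% / 97% against 92% / 99.6%.

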#### 1.2 Secondary Objectives

- A. To evaluate the ability of **locally administered** TLR agonist (R848 gel) to activate innate immune cells at the gp100 (g209-2M) **vaccine site**.
- B. To evaluate the ability of R848 gel, administered at the **tumor site**, to:
  - i. Induce inflammation and upregulation of adhesion molecules on tumor vasculature
  - ii. Enhance T-cell infiltration into tumor
  - iii. Generate T-cells against additional tumor antigens, not present in the vaccine (i.e., antigen spreading).
  - iv. Mediate clinical response with measure of objective tumor response rate and progression free survival.

C. To assess the association between clinical response and laboratory parameters of T-cell priming, T-cell migration to tumor, and inflammation at the vaccine and tumor sites.

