### **6.0 Treatment Plan**

All patients will receive the class I, HLA-A2 restricted gp100(g209-2M) peptide vaccine. Patients who are HLA-DP4 positive will also receive the class II restricted MAGE-3 peptide, in separate extremities. This will allow us to generate melanoma-specific CD8+ and CD4+ T-cells. The gp100(g209-2M) immune response will be our primary endpoint for assessment of T-cell priming, since we have extensive previous experience with this vaccine and believe that CD8+ responses are critical to the development of a strong antitumor immune response. The MAGE-3 peptide will be given in order to stimulate antigen-specific CD4+ T-cells, which we believe are also important in the generation of strong antitumor immunity. Patients positive for both HLA types will

receive both vaccines, gp100(g209-2M) and MAGE-3, for eight weeks. Patients who are HLA-A2 positive and HLA-DP4 negative will receive only the gp100 peptide for 8 weeks. There will be two arms in Part 1: Arm A is the peptide vaccines plus the TLR7/8 agonist, R848 and Arm B is the peptide vaccines only. All patients will be randomized to either Arm A or Arm B by CORe during the registration process. The randomization will be stratified by cohort (metastatic disease or adjuvant). In Arm A, R848 gel will be applied to the gp100(g209-2M) vaccine injection site immediately following the injection. The R848 gel will be allowed to air dry for 30 minutes and then covered with a gauze dressing. All vaccines will be administered subcutaneously and intradermally. The gp100(g209-2M) peptide will be administered in the same extremity weekly (every 7 days +/- 2 days) for 8 weeks. Similarly, in a separate extremity of eligible patients, the MAGE-3 peptide will be administered weekly (every 7 days +/- 2 days) for 8 weeks. Each syringe (a total of 4, 2 for gp100 and 2 for MAGE-3) will contain 1ml of peptide vaccine; 0.5ml of the vaccine in each syringe will be administered intradermally and the other 0.5ml will be administered subcutaneously at each injection site for a total of 4 sites.

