## 11.0 Statistical Considerations

### Overview

This is a randomized phase II trial enrolling melanoma patients who are HLA-A2+ with or without HLA-DP4+. Patients of two separate types will be enrolled in separate cohorts. One cohort includes patients who are NED but at high risk for recurrence. The second cohort will include patients with non-visceral metastatic disease and must have at least two evaluable and biopsiable lesions to be eligible for the trial.

The trial will have two parts. In Part 1 (both cohorts), we will fairly randomize patients to receive either the gp100(g209-2M) +/-MAGE3 peptide vaccine plus a topical TLR 7 /8 agonist, R848, (Arm A) or the gp100(g209-2M) +/- MAGE3 vaccine alone Arm B). The randomization will be stratified by cohort. A total of 48 patients will be enrolled, 24 per arm. All patients will receive the gp100(g209-2M) vaccine (those who are HLA-DP4 + will also receive the MAGE3 vaccine) weekly (for 8 weeks) and the patients randomized to receive R848 gel will have the gel applied to the gp100(g209-2M) vaccine site weekly.

After 8 weeks of treatment on Part 1, Part 2 of the trial begins. In Part 2 (only patients in the metastatic disease cohort), the treating physician will divide the area of cutaneous lesions into regions, Region A and Region B and designate the two regions to receive or not to receive R848. At least one lesion will be randomly assigned to receive R848 from weeks 8 through 24, and one will not. One lesion from each region will be chosen for biopsy as outlined in section 7.3. If a patient has more than two evaluable lesions, we will stratify by lesion size to assure that the lesions will be comparable.

As a safety measure, if a patient's untreated lesions grow while treated lesions are stable or shrink, all lesions will be treated with R848. This will occur after the assessment of the primary endpoints of the study, so it will not affect the analysis of these endpoints.

In April 2015, the trial is being further modified to add an additional 20 patients with metastatic disease, all of whom will receive the the gp100(g209-2M) +/-MAGE3 peptide vaccine plus R848 (Arm C). These patients will not be part of the primary comparative study analysis of T-cell responses in the blood. The purpose of these patients is to provide additional information on characterizing tumor response, defined as at least a 50% shrinkage in tumor size by irRC criteria.

### Part 1

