The primary outcomes for part 2 of the trial are immune cell infiltration for pDCs, mDCs, and NK cells in the tumor biopsy samples. This can be assessed in the metastatic disease cohort only, since those subjects in the adjuvant therapy cohort are free of disease. Tumor samples will be taken as outlined in section 7.3. Three different types of analyses will be performed on these tumor biopsies: (1) Immunohistochemistry (IHC) for the degree of pDC, mDC, and NK cell infiltration, (2) Flow cytometry (FACS) analysis for infiltrating melanoma specific CD8+ T cells, and (3) Quantitative RT-PCR (qRT-PCR) assays for IFN- $\gamma$ , IFN- $\alpha$  (and other type I interferons), IL-12, and TGF- $\beta$ . For each of these outcomes, we will determine the differences in each of these parameters between the pretreatment and post-treatment samples for each of the biopsied lesions for each patient. Mixed-effect models will be fit for each parameter to assess the effects of treatment, time, and the initial randomization to gp100(g209-2M) +/- MAGE-3 vs. gp100(g209-2M) +/- MAGE-3 +R848. If there is no evidence of an effect due to the initial randomization in Part 1, the changes from baseline for the R848 treated lesion and the untreated lesion will be calculated, and these differences will be compared between the R848 and non-R848 lesions by using a paired t-test.

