To evaluate the association between clinical response and laboratory parameters of T-cell priming, T-cell migration to tumor, and inflammation at the vaccine and tumor sites we will explore the relationship between immune cell activation measures at the vaccine site (vaccine site measures) and at the tumor site (tumor site measures). Additionally we will assess the effect of the TLR agonist R848 upon clinical response. Clinical response will be assessed using the immune-related response criteria (irRC) and will be assessed at week 8, 16, and every 8 weeks thereafter. Since both vaccine site measures and tumor site measures are continuous variables we will assess association between these two types of variables using Pearson's or Spearman's correlation coefficient. In addition, we will use logistic regression to model the relationship between either vaccine site or tumor measures and best clinical response assessed over a 16 weeks period after initial vaccination.

To assess the association between R848 treatment on lesions and response, the irRC will be used to assess response separately by lesion type (lesions receiving or not receiving R848 cream). That is, using the irRC, we will, for each patient, assess if the lesions not treated with R848 cream responded and also determine if the lesions treated with R848 cream responded. Thus, for each patient we will record 4 possible joint outcomes ++, +-, -+, and --, where the ++ indicates that both lesions receiving and not receiving R848 cream responded; -- indicates neither types of lesions responded. Similarly +- and -+ indicate one type of lesion responded while the other did not. We will assess differences between treatments (based on within patient differences) using McNemar's test. A statistically significant difference with respect to the McNemar's test will indicate if cream administered to the lesion results in improved outcome (i.e., immune-related response criteria) relative to lesions for which cream was not administered.

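### The vaccine-site/tumor-site correlations carry no arm term, so if arm also shifts tumor-site measures, a pooled coefficient can be non-zero with no within-arm association

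*Combined protocol and SAP*

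**What the plan says.** Objective C in section 1.2 is "To assess the association between clinical response and laboratory parameters of T-cell priming, T-cell migration to tumor, and inflammation at the vaccine and tumor sites". Section 11.0, Overview of Analysis of Secondary Endpoints, carries this out in two steps. First, "we will explore the relationship between immune cell activation measures at the vaccine site (vaccine site measures) and at the tumor site", and for that "we will assess association between these two types of variables using Pearson's or Spearman's correlation coefficient". Second, "we will use logistic regression to model the relationship between either vaccine site or tumor measures and best clinical response". Neither step names arm as a covariate or stratum, and neither gives a significance level.

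The arms differ at the vaccine site by design. Section 6.0 states "In Arm A, R848 gel will be applied to the gp100(g209-2M) vaccine injection site immediately following the injection", and Arm B receives the peptides only. The section 11.0 Overview repeats that "the patients randomized to receive R848 gel will have the gel applied to the gp100(g209-2M) vaccine site weekly". Raising innate activation at that site is secondary objective A.

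Elsewhere the plan does attend to arm. For the tumor-biopsy parameters in Part 2 of section 11.0, "Mixed-effect models will be fit for each parameter to assess the effects of treatment, time, and the initial randomization". Arm is dropped there only for the paired t-test, and only if no effect of the Part 1 randomisation is seen. The blood parameters are to be plotted separately by arm. Neither provision is carried over to the correlations.

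**The concern.** A correlation taken over two groups mixes two things: the association inside each group, and the difference between the group means. Here the groups are the randomised arms, and one of the two correlated variables is the one the randomised gel is meant to raise. If arm also raises the tumor-site measure, the means of both variables move together. The pooled coefficient is then positive even when, among patients treated alike, vaccine-site inflammation says nothing about the tumor.

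What is at stake is interpretation. A reader of the trial report would probably take such a correlation to mean that patients with more vaccine-site inflammation have more tumor infiltration. The pooled coefficient cannot tell that apart from the arm comparison, which the plan already estimates directly. The ambiguity grows with the treatment effect, so it is greatest when the trial's hypotheses are right.

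**Working it through.** **Inputs from the documents.** Tumor biopsies are taken in the metastatic cohort only (section 7.3). Part 2 of section 11.0 expects 24 such patients and 17% loss: 24 × 0.83 = 19.9, hence 20, or 10 per arm. The plan gives no figure for the correlation itself.

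**The plan's own figure for these patients.** Part 2 claims 80% power for 1.2 SD with a one-sided 5% two-sample t-test. With 10 per arm there are 18 degrees of freedom and the noncentrality is 1.2 × √(10/2) = 2.68. The noncentral t gives 82.5% power, against 78.5% at 9 per arm. The effect detectable at 80% is 1.156 SD, which rounds to 1.2. The figure reproduces.

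**Assumptions.** Let dv and dt be the arm shifts at the vaccine site and tumor site, in within-arm SDs. The documents give neither. The range used is dv = 1 to 2 and dt = 0 to 1.2. The values 0.73 and 1.2 are the plan's effect sizes for other contrasts (the Part 1 blood tetramer comparison and the Part 2 R848 effect), used only as convenient magnitudes. Data are normal, the within-arm correlation is zero, and the test is two-sided at 5%.

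**Pooled correlation from arm alone.** With p the proportion receiving gel at the vaccine site:

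r = p(1−p)·dv·dt / √[(1 + p(1−p)dv²)(1 + p(1−p)dt²)]

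For p = 0.5, dv = 2, dt = 1.2: 0.25 × 2.4 / √[(1 + 1)(1 + 0.36)] = 0.60 / 1.649 = 0.36. If dt = 0 the numerator, and so r, is zero whatever dv is.

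**Rejection rates, 10 + 10 patients.** There were 40,000 simulated trials per cell, except 6,000 for the dv = 1 rows, where only Spearman was run.

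| dv | dt | r from formula | pooled Pearson | pooled Spearman |
|---|---|---|---|---|
| 1.2 | 0 | 0 | 4.9% | 5.0% |
| 2 | 0 | 0 | 4.9% | 4.9% |
| 1 | 0.73 | 0.15 | – | 10% |
| 1 | 1.2 | 0.23 | – | 17.5% |
| 1.2 | 0.73 | 0.18 | 11.9% | 11.9% |
| 1.2 | 1.2 | 0.26 | 21.0% | 21.5% |
| 2 | 0.73 | 0.24 | 18.9% | 19.4% |
| 2 | 1.2 | 0.36 | 38.2% | 40.1% |

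**After adjustment for arm.** The partial Pearson and within-arm-centred Spearman tests reject 4.7% to 5.5% of the time in these cells.

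**If Arm C were included** (30 with gel, 10 without, Arms A and C treated as one group): at dv = 2, dt = 1.2 the pooled rates are 50% (Pearson) and 44% (Spearman). Arm-adjusted Spearman gives 5.5% in that cell. It reaches 6.6% at the most extreme shifts tried (dv = 3, dt = 2), so with unequal groups the rank adjustment is close to nominal but not exact.

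**The case against.** Several points against the concern have force.

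- **Pooling is inferred from silence.** A reader might conclude that the plan says the arms are combined. It does not; it leaves the handling of arm unspecified. Given the attention to arm elsewhere, the analyst might adjust anyway. This stands as a description. It does not remove the problem, because the text followed literally yields one unadjusted coefficient.
- **No error rate is breached.** A reader might infer that a planned 5% level is exceeded. The 5% statements in section 11.0 belong to the signed-rank test and the mixed models. The correlations are exploratory with no stated level, so the rejection rates above rest on an assumed test. The displacement of r does not depend on any level.
- **A vaccine-site difference is not enough.** With no arm shift at the tumor, the rate stays at about 5%. The documents predict no particular shift of tumor measures from gel at the vaccine site. The Part 2 contrast is R848-treated against untreated lesions, and patients from both Part 1 arms receive gel on tumors. The priming pathway bears most directly on T-cell measures, less on pDC, mDC or NK infiltration. All of this stands.
- **The pooled coefficient is not merely an artefact.** If R848 acts on the tumor through vaccine-site activation, randomised variation in that activation is the exposure of interest, and part of the pooled correlation is the hypothesised pathway. Conditioning on arm answers a different question. This stands, and is why both results should be shown.
- **Adjustment is not free in the logistic model.** At the 5% and 22% response rates quoted for Arms A and C, 20 to 30 patients give about 1 (20 × 0.05) to 7 (30 × 0.22 = 6.6) responders. Requiring an arm term could make the fit unstable. This stands.

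**Conclusion.** The concern holds as a conditional one. The plan correlates vaccine-site with tumor-site measures without saying how arm is handled, although arm is the randomised cause of one of them. If arm also shifts the other, the pooled coefficient can arise with no within-arm association. At 10 + 10 patients the rejection rate is about 5% with no tumor shift. For tumor shifts of 0.73 to 1.2 SD and vaccine-site shifts of 1 to 2 SD it is about 10% to 40%. The shifts and the two-sided 5% test are assumptions; in particular, no section supports a 2 SD vaccine-site shift.

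The documents do not support the stronger reading that a false-positive rate of 20% to 40% is to be expected, or that any pooled correlation would be spurious. Nor do they say that Arm C enters this analysis, so the 30 + 10 results are only an illustration. The point concerns an exploratory secondary analysis and touches no primary endpoint.

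**What to change.** In section 11.0, Overview of Analysis of Secondary Endpoints:

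- Report the arm-adjusted vaccine-site/tumor-site correlation (partial Spearman, or Spearman stratified by Part 1 arm) next to the pooled one.
- State that the pooled value mixes the arm effect with the within-arm association, and that any claim that vaccine-site inflammation itself predicts tumor-site measures rests on the adjusted result.
- State whether Arm C patients are included and, if so, treat Arm C as its own stratum, since it is not randomised.
- Add arm to the logistic model only as a sensitivity analysis, when the number of responders allows it.

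The change is SAP wording and needs no new data. It costs one degree of freedom per added stratum. With about 10 patients per arm, and biopsies that may be declined or not feasible, the adjusted estimate will be imprecise, and the report should say so and give an interval.
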